| intervention | Unlikely | The AE is doubtfully related to the intervention |
| Related to | Possibly | The AE may be related to the intervention |
| intervention | Probably | The AE is likely related to the intervention |
| | Definitely | The AE is clearly related to the intervention |

NHLBI-IRB and CD reporting

Serious Events

Reports to the IRB and CD: The PI must report Serious UPs, and Serious PDs to the IRB and CD as soon as possible but not more than 7 days after the PI first learns of the event using the NIH Problem Report Form.

Non-serious Events

Reports to the IRB and CD: The PI must report all UPs that are not Serious to the IRB and CD, and PDs that are not Serious to the IRB, not more than 14 days after the PI first learns of the event using the NIH Problem Report Form.

Deaths

Deaths possibly, probably, or definitely related to study procedures will be reported to the Clinical Director within 7 days after the PI first learns of the event.

Reports at the time of continuing IRB review: At continuing review, the PI will provide to the IRB a summary of:

- All UPs
- All PDs
- All AEs (except for those granted a waiver of reporting)

Waiver of Reporting: The following adverse events will be listed in the consent and not reported to the IRB:

- Vasovagal symptoms during blood draws (expected frequency 50%).
- Transient bruising at the site of blood draws (expected frequency 50%).
- Hunger, headache, fatigue, or irritability during fasting (expected frequency 50%).

13. Human Subjects Protections

Rationale for Subject Selection

Subjects of both genders will be considered for inclusion in this study. There will be no racial, ethnic, or gender discrimination. Cognitively impaired and institutionalized persons will not participate in this study. Recruitment, enrollment and compensation of NIH employee subjects will be consistent with NIH Manual Chapter 2300-630-3: Leave Policy for NIH Employees.

Rationale for the Exclusion of Children

Subjects under 18 years of age will not be considered for inclusion in this protocol because there is no direct benefit from participating in this study and the 24-hour fast and volumes of blood levels drawn exceed minimal risk for children.

Rationale for the Exclusion of Pregnant Women

Subjects must not be pregnant or actively seeking pregnancy in order to participate in this study. NR has not been determined to be safe in pregnancy or breastfeeding. A recognized form of contraception must be used by subjects while enrolled. Contraception use will be determined during telephone screening and confirmed at the screening visit.

Rationale for the Exclusion of Cognitively Impaired Subjects

Subjects with cognitive impairment will not be considered for inclusion because there is no direct benefit from participating in this study.

Risk/Benefit Assessment

The research involves greater than minimal risk to subjects, with no prospect of direct benefit, but is likely to yield generalizable knowledge (45 CFR 46.102).

Inclusion of NIH Staff

- NIH staff (employees, NIH contractors, special volunteers, guest researchers, and trainees) may voluntarily participate in this protocol.
- Recruitment, enrollment and compensation of NIH staff will be consistent with the Guidelines for the Inclusion of Staff in NIH Intramural Research Studies (December 2015) (Appendix A of SOP 14F) and NIH Policy Manual Chapter 2300-630-3,:"Leave Policy for NIH Employees Participating in NIH Medical Research Studies" (Appendix B of HRPP SOP 14F,).

 If the individual requesting to participate in the protocol is a co-worker, the consent from the NIH staff member (co-worker) will not be obtained by the staff member's direct supervisor but by another research staff member approved for obtaining informed consent, and who is also not a co-worker.
- Neither participation nor refusal to participate as a subject in this protocol will have an effect, either beneficial or adverse, on the participant's employment or position at NIH. However, all subjects will be made aware that there are limits to these protections.
- The PI, through the consenting staff member will make the "NIH Information Sheet on Staff Research Participation" available to staff members who are considering enrolling in research. (SOP 14F, Appendix C; also in Appendix A of the protocol)

Risks and Discomforts

- *Phlebotomy:* Standard precautions for obtaining human blood samples will be taken. Transient discomfort and minor bruising may occur at the phlebotomy site. Vasovagal symptoms can occur during blood drawing. Blood samples will be obtained by venipuncture. Blood samples will be obtained by a nurse, physician, or other skilled individual. A total of 440 mL of blood with be drawn for this study. The quantities of blood to be drawn for research purposes will be consistent with the CC policy as provided in Medical Administrative Series (MAS) 95-9 (revised 05/29/2012):
 - a. Subjects 18 years of age or older (index cases and relatives): It is estimated that 100 mL will be drawn in one blood draw (but never exceeding 10.5 mL/kg or 550 ml (whichever is smaller) over any 8-week period.
- 24-Hour Fast: Subjects may experience hunger, headache, fatigue, or irritability during fasting. Subjects will be instructed not to take Acetaminophen (Tylenol®).

Amendment F, May 22, 2018 [name], PhD Acetaminophen is usually well tolerated in prescribed dose, but when taken during fasting may cause of drug-induced liver disease and acute liver failure. The first symptoms of liver damage are seen in the initial 12 to 24 hours or so after ingestion and include nausea and vomiting.

• *Urine collection:* There is no risk associated with this procedure.

Nicotinamide Riboside: NR is a dietary supplement that is currently available for commercial use with no safety concerns noted to date. Consecutive doses of 1000mg daily of NR has not been reported in humans although there is currently an ongoing study at the University of Colorado using 1000 mg daily for 6 weeks. Based on the structural similarities between NR and nicotinamide, and that nicotinamide is a downstream metabolite of NR digestion, it is assumed that any unexpected adverse effects of NR may be similar to those associated with nicotinamide intake. The safety profile of nicotinamide has been well established in multiple species and provides reasonable certainty that the administration of doses of NR up to 1000 mg will not result in an adverse health effect. No significant adverse effects have been reported in clinical trials which have used doses up to the equivalent of 3000 mg/day for up to 3 years to evaluate the possible benefits of nicotinamide administration to patients with or at risk of developing Type 1 diabetes. ^{10, 11} In addition, doses of 25 and 42 mg/kg bw/day had no effect on a variety of biochemical parameters, such as those that assessed liver and kidney function.

Consent Processes and Documentation for Research Subjects

Each participant will receive an oral and written explanation of the goals, procedures, and risks of this study. The Principal Investigator and those Associate Investigators who are listed on the cover page of the protocol with an asterisk next to their name may obtain informed consent from research participants. Consent will be obtained at the NIH Clinical Center. The original, signed informed consent document will be placed in the medical record, and the subject will receive a signed copy of the informed consent document.

If there is an unexpected enrollment of a non-English speaking research participant for which there is no translated extant IRB approved consent document, the principal investigator and/or those authorized to obtain informed consent will use the Short Form Oral Consent Process as described in MAS Policy M77-2, 45 CFR 46.117 (b) (2). The summary that will be used is the English version of the extant IRB approved consent document.

We request prospective IRB approval of the use of the short form for up to a maximum of 2 participants in a given language and will notify the IRB at the time of continuing review of the frequency of the use of the Short Form. Should we reach the threshold of 2, we will notify the IRB of the need for an additional use of the Short Form and that we will have that consent document translated into the given inherent language.

Consent Processes and Documentation for NIH Staff

If the individual requesting to participate in the protocol is a co-worker, the consent from the employee (co-worker) will not be obtained by the research coordinator or the staff member's direct supervisor but by another research staff member who is approved for obtaining informed consent, and who is also not a coworker. NIH staff will be given the NIH Information Sheet on *Staff Research Participation* (See appendix A) to help them understand the possible consequences of participation.

14. Conflict of Interest

None of the members of the research team reported a potential conflict of interest. The National Institutes of Health reviews NIH staff researchers at least yearly for conflicts of interest. The following link contains details on this process http://ethics.od.nih.gov/forms/Protocol-Review-Guide.pdf. This protocol has a CRADA with ChromaDex, Inc.

15. Reimbursement for Travel

As the study populations will be local, reimbursement for travel, food, and lodging will not be provided.

16. Financial Compensation

Subjects will be compensated for procedures that are performed that are of no direct benefit to the subject, although would be of generalizable benefit to enhance our understanding of Participants will be compensated as described in the table below:

| Procedures | Inconvenience Units | Compensation per procedure | Frequency | Total Compensation |
|---|------------------------|----------------------------|-----------|-----------------------|
| Medical History and physical examination | 2.5 | \$25.00 | 1 | \$25.00 |
| Outpatient Visit (first hour) | 2 | \$20.00 | 3 | \$60.00 |
| Outpatient Visit (additional hours up to 4 hours) | 1 | \$10.00 | 8 | \$80.00 |
| Screening Blood Draw (if needed) | 1 | \$10.00 | 1 | \$10.00 |
| Research Blood Draw | 2.5 | \$25.00 | 4 | 100.00 |
| 24-Hour Fast | 15 | \$150.00 | 2 | \$300.00 |
| Urine Sample | 1 | \$10.00 | 3 | \$30.00 |
| Drug administration, General | 2 | \$20.00 | 14 | \$280 |
| | \$885.00 | | | |

17. References

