Normal volunteers will be enrolled on this 3-5 week study that includes 3 visits to the NIH Clinical Center. Subjects may be contacted by telephone, text or email to verify study compound compliance, for AE/safety assessment and to remind subjects to initiate the 24-hour fast prior to Visit #2 and Visit #3. Email communications will be made through the NIH medical secure email system unless the patient declines its' use and requests standard unsecure email. A schematic showing the outline of the overall study is shown below.

The variable length of the washout and study arms phase is to allow flexibility for the scheduling of subject visits. The prior pharmacokinetic studies support that 7 days is more than sufficient to restore NAD⁺ levels to baseline.

The following actions will be undertaken at the defined visits:

Arm 1

Screening/Visit 1:

- Subjects will be screened for inclusion or exclusion.
- Baseline screening laboratories performed.
- Pregnancy testing in women of childbearing potential.

- Eligible subjects will be randomized to placebo (i.e. sugar tablet) or 1 gram of NR daily. The study compound start date will be determined at this visit. Start date will be within one week of screening visit.
- Instruct subject on study compound administration, reinforce maintenance of stable diet and activity level during the study participation period, and review the time of the breakfast on day 6 (+3 days, if needed), prior to initiating the 24-hour fast.

Day 1 of Arm 1 study compound administration.

A member of the research team may contact study subjects:

- to remind them which day to initiate therapy
- to remind subjects of the 24-hour \pm 2hr fast

Visit 2: Day 7 (+ up to 3 days, if needed) of Arm 1 study compound administration

- Subjects will arrive at the Clinical Center after a 24-hour fast ± 2 hours with the
 exception of drinking water starting the morning of day 6 (+ up to 3 days, if
 needed).
- A pill count will be performed to evaluate compliance.
- Fasting blood draw for hepatic panel, acute care panel, insulin, growth hormone, complete blood count, serum immune cell studies and to measure NAD levels.
- Urine collection for ketones
- Administer day 7 (+ up to 3 days, if needed) Arm 1 placebo/NR capsules.
- A 500 caloric meal will be eaten.
- Refed blood-draw for insulin, growth hormone, glucose, serum immune cell studies and to measure NAD levels three hours ± 30 minutes after fixed caloric meal (metabolic kitchen).

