- Subject educated about washout period.
- New bottles of study compound for Arm 2 dispensed.

Washout period of 7-14 days

Arm 2

Day 1 of Arm 2 study compound administration

A member of the research team may contact study subjects:

- to remind them which day to initiate therapy
- to remind subjects of the 24-hour \pm 2hr fast

Visit 3: Day 7 (+ up to 3 days, if needed) of Arm 2 study compound administration

- Subjects will arrive at the Clinical Center after a 24-hour fast \pm 2 hours with the exception of drinking water starting the morning of day 6 of the second study arm.
- A pill count will be performed to evaluate compliance.
- Fasting blood draw for hepatic function panel, acute care panel, complete blood

count, insulin, growth hormone, serum immune cell studies and to measure NAD levels.

- Urine collection for ketones
- Administer day 7 of Arm 2 placebo/NR capsules.
- A 500 caloric meal will be eaten.
- Refed blood draw for insulin, growth hormone, glucose, serum immune cell studies and to measure NAD levels three hours ± 30 minutes after fixed caloric meal (metabolic kitchen).

Off Treatment (Supplement):

Subjects will be considered off treatment (supplement) after completion of Arm 2 study pills.

Follow up:

We will follow up the subjects for 30 days after completion of Arm 2 study pills for any AEs. Subject will be instructed to the contact research team if any symptoms develop during this 30 day period.

Off Study:

Subject will be taken off study 30 days after completion of Arm 2 study pills. If a subject doesn't report any AEs, we will take him/her off study on day 30 after completion of Arm 2 study pills. If a subject reports any AEs during the 30-day follow up period then we will adjust off study date upon resolution/returning to the baseline of the AEs.

Randomization and dispensing of study pills:

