Multiple lines of non-clinical data suggest that NR intake does not present any potential risks and should be well tolerated in human subjects. The dose proposed for this study is within the doses tested in non-clinical studies of mice for up to 4 months, and are 300-fold below the daily dose that was given in rats in a 14-day dose range finder study.

Nicotinamide, an expected metabolite of NR, is a molecule that is considered of low toxicity in food by several regulatory agencies including the United States Food and Drug Administration (FDA) and the European Food Safety Authority (EFSA).

Because nicotinamide is a putative metabolite of NR in humans, understanding the safety profile of nicotinamide is relevant when assessing the safety of NR in human subjects.

Based on the structural similarities between NR and nicotinamide, and that nicotinamide is a downstream metabolite of NR digestion, it is assumed that any unexpected adverse effects of NR may be similar to those associated with nicotinamide intake. However, no significant adverse

effects have been reported in clinical trials which have used doses up to the equivalent of 3000 mg/day for up to 3 years to evaluate the possible benefits of nicotinamide administration to patients with or at risk of developing Type 1 diabetes ^{10, 11}. In addition, doses of 25 and 42 mg/kg bw/day had no effect on a variety of biochemical parameters, such as those that assessed liver and kidney function.

In summary, careful analysis of all the non-clinical information available on NR has not revealed any potential serious toxicity that would preclude its use in healthy subjects.

Common name: Nicotinamide Riboside Chloride

Product name: Niagen

Chemical name: 3-(Aminocarbonyl)-1-β-D-ribofuranosyl-pyridinium chloride (1:1)

Dose: 1000mg daily for 7-10 days

Route of administration: oral

Dosing instructions: (4) 250mg study capsules daily after breakfast.

Supply: Drug will be supplied by ChromaDex

Manufactured by: W.R. Grace & Co. [name],

USA

Toxicology: None known.

Drug Interactions: None known.

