Protocol Deviation (PD): Any change, divergence, or departure from the IRB approved research protocol.

Non Compliance: The failure to comply with applicable NIH HRPP policies, IRB requirements, or regulatory requirements for the protection of human research. Noncompliance may be further characterized as:

Serious non-compliance: Non-compliance that:

- a. Increases risks, or causes harm, to participants.
- b. Decreases potential benefits to participants.
- c. Compromises the integrity of the NIH HRPP.
- d. Invalidates the study data.

Continuing non-compliance: Non-compliance that is recurring. An example may be a pattern of non-compliance that suggests a likelihood that, absent an intervention, non
Page 16 of 25

compliance will continue. Continuing noncompliance could also include a failure to respond to IRB requests to resolve previous allegations of non-compliance.

Minor (non-serious) non-compliance: Non-compliance that, is neither serious nor continuing.

Adverse Event Management

The principal investigator and medical advisory investigator, or designee, will be responsible for assessing adverse events. Information on adverse events will be solicited from subjects through questions from study personnel and/or information volunteered by the subject. Adverse events will be captured from the start of the first pill taken (day 0) until 30 days following the last pill taken. Following this period, only serious adverse events that are unexpected and related to study pills will be reported. All AEs, regardless of severity, will be recorded, graded, assigned an attribution, verified, and followed until satisfactory resolution.

In the event of any treatment-related SAEs, enrollment will be suspended until discussed with the IRB and Clinical Director.

Grading and Attribution of Adverse Events

Mild: Awareness of sign or symptom, but easily tolerated. Not expected to have a clinically significant effect on the patients overall health and well-being. Not likely to require medical attention.

Moderate: Discomfort enough to cause interference with usual activity or affects clinical status. May require medical intervention.

Severe: Incapacitating or significantly affecting clinical status. Likely requires medical intervention and/or close follow-up.

Attribution of Adverse Events

| Relationship | Attribution | Description |
|--------------|-------------|--|
| Unrelated to | Unrelated | The AE is clearly NOT related to the intervention |

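### No contact is required in the 30-day safety follow-up, and Sections 5 and 12 start that follow-up from different dates

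*Combined protocol and SAP*

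**What the plan says.** Section 5 (Follow up) sets the period: "We will follow up the subjects for 30 days after completion of Arm 2 study pills for any AEs". The procedure for it is one sentence: "Subject will be instructed to the contact research team if any symptoms develop during this 30 day period".

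Section 5 (Off Study) then gives the closing rule: "Subject will be taken off study 30 days after completion of Arm 2 study pills", and "If a subject doesn't report any AEs, we will take him/her off study on day 30 after completion of Arm 2 study pills". If an AE is reported, the off-study date moves to its resolution or return to baseline. The final Arm 2 dose is given in clinic at Visit 3, and no visit, call or laboratory test is listed after that.

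Two other places bear on how AEs are found:

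- Section 5, opening paragraph: "Subjects may be contacted by telephone, text or email to verify study compound compliance, for AE/safety assessment". No dates are attached to this contact.
- Section 12 (Adverse Event Management): "Information on adverse events will be solicited from subjects through questions from study personnel and/or information volunteered by the subject". The window is stated next: "Adverse events will be captured from the start of the first pill taken (day 0) until 30 days following the last pill taken".

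Section 11 foresees withdrawal for low adherence, pregnancy or breastfeeding, or significant medical symptoms.

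**The concern.** Section 12 undertakes to capture every AE up to 30 days after the last pill. Section 5, which staff will follow day to day, leaves the first move in those 30 days to the subject and closes the record when the subject stays silent. Someone who had an event and did not call leaves the study in the same way as someone who had none.

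The two sections also use different starting points. Section 5 ties both follow-up and the off-study date to completion of Arm 2. A subject withdrawn in Arm 1 or in the washout has no such date, so Section 5 gives that subject neither a follow-up period nor an off-study date.

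What is at stake is the completeness of the safety record. Section 13 classes the study as greater than minimal risk with no prospect of direct benefit. Section 12 suspends enrollment for any treatment-related serious AE and promises the IRB an AE summary at continuing review. Both depend on events being found.

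**Working it through.** **Inputs**

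- Treatment arm: 7 to 10 days (Section 8: "Dose: 1000mg daily for 7-10 days"; Section 5 gives day 7 plus up to 3 days).
- Washout: 7 to 14 days (Section 5).
- Follow-up: 30 days (Sections 5 and 12).
- Stated study length: 3 to 5 weeks (Section 5).

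**Step 1. Reproduce the stated study length.** Span = Arm 1 + washout + Arm 2.

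- Shortest: 7 + 7 + 7 = 21 days = 3.0 weeks.
- Longest: 10 + 14 + 10 = 34 days = 4.9 weeks.

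This agrees with the stated 3 to 5 weeks.

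**Step 2. AE window.** Window = span + 30 days.

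- Shortest: 21 + 30 = 51 days.
- Longest: 34 + 30 = 64 days.

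**Step 3. Share of the window with no required contact.** Share = 30 / window.

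- Shortest schedule: 30/51 = 58.8%.
- Longest schedule: 30/64 = 46.9%.

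Other ways of counting change little. Taking the stated upper limit of 5 weeks (35 days) gives 30/65 = 46.2%. Counting elapsed days (20 to 33) gives 30/50 = 60.0% to 30/63 = 47.6%. About half holds throughout.

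**Step 4. Is contact required anywhere else?** Section 5's opening paragraph permits contact for AE assessment without requiring it. Section 12 joins questioning and volunteered reports with and/or, so volunteered reports alone would satisfy it. Neither creates a scheduled query after Visit 3.

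**Step 5. Compare the anchors.**

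| Subject | Section 5 follow-up starts | Section 12 window ends |
|---|---|---|
| Completes both arms | Completion of Arm 2 pills | 30 days after that same pill |
| Withdrawn in Arm 1 or washout | No date | 30 days after the last Arm 1 pill |
| Withdrawn during Arm 2 | No date, if Arm 2 is not completed | 30 days after the last Arm 2 pill |

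The sections agree only for subjects who complete Arm 2.

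**Step 6. Compare the two periods.** After the last Arm 1 dose at Visit 2, the subject is seen again at Visit 3, which is 7 + 7 = 14 to 14 + 10 = 24 days later, with hepatic, acute care and blood count tests. After the last Arm 2 dose no further visit is listed.

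**The case against.** The strongest reply is that the plan as a whole already provides for this. Section 12 governs AE collection, names questioning by staff as one of its methods, and runs to 30 days after the last pill in whichever arm that was taken. Section 5 allows telephone, text or email contact for AE assessment. Subjects withdrawn for symptoms are by definition known to the team, pregnancies are monitored to their conclusion, and every recorded AE is followed to satisfactory resolution.

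Much of this stands. A reader might infer that the follow-up asks subjects nothing; the documents permit questioning, so the accurate statement is that none is scheduled or required. A reader might also infer that early withdrawals fall outside AE capture; Section 12's window covers them, and the gap is in Section 5 only. A reader might infer that silence is entered as no AE. Section 5 sets an off-study date and does not say what is recorded.

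The 47% to 59% is also a share of calendar days, not of expected events. All dosing and both fasts come before the 30 days begin. Section 5 holds that 7 days is ample for NAD⁺ to return to baseline, so on the protocol's own reasoning about 30 − 7 = 23 of the 30 days follow that return.

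What the reply does not remove is that permission to ask is not a requirement to ask, and that Section 5's operating rule conflicts with Section 12's window for anyone who does not complete Arm 2.

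**Conclusion.** The point holds as a gap in required safety follow-up together with an inconsistency between two sections. AE capture over 30 of 51 to 64 days (47% to 59% of the window, all after dosing ends) can rest on spontaneous reports alone, and Section 5's anchor has no meaning for a subject withdrawn before completing Arm 2. The arithmetic uses only the protocol's own durations and assumes that both arms are completed on schedule.

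Two stronger conclusions are tempting and are not supported. One is that events are undercounted by a known fraction: that needs a capture rate for spontaneous reporting, and the documents give none. The other is that the trial's findings are put in doubt. Tolerability is not among the objectives in Section 4 or the analyses in Section 10. Ascertainment after the last dose does differ by period, but treatment order is randomized and blinded, so this does not systematically favor NR or placebo. The IL-1β conclusion is unaffected. This is a worthwhile, low-cost improvement to safety capture.

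**What to change.** 1. In Section 5 (Follow up and Off Study), replace completion of Arm 2 pills with the last pill taken, as Section 12 already has it, so that subjects withdrawn early have a defined follow-up period and off-study date.
2. Require one documented AE query at about day 30 after the last pill, by telephone or email (channels Section 5 already allows), for every subject including those withdrawn early, before the subject is taken off study.
3. If the subject cannot be reached, note that in the record, so that a subject not reached can be told apart from one who was asked and reported nothing.

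The cost is protocol wording and about 42 short contacts by existing staff, one for each subject under the enrollment ceiling of 42. Slightly more minor AEs will be recorded. The length of the AE window does not change for subjects who complete Arm 2.
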